## **4.0 Eligibility Criteria**

### **4.1 Inclusion Criteria**

[figure not shown]
- Between the ages of 18 and 80 years old
- Ability and willingness to independently consent to treatment and study participation
- Uncomplicated medical history (ASA I and II)
- No allergies to local anesthetics/sulfites (confirmed or self-reported)
- Not taking any medications that may affect the proper assessment of the anesthetic (OTC analgesics within 6 hours of treatment)
- Not requiring nitrous oxide during treatment
- No active pathology in the injection area or any other pre-existing conditions that may compromise an accurate collection of data per PI's review of current and previous 30 days of medical history
- Must be experiencing signs of irreversible pulpitis (mild, moderate, or severe) in a vital mandibular posterior tooth at the time of conducting the study

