## 6.0 Enrollment/Randomization

Potential research subjects will be pooled from patients scheduled to receive an endodontic evaluation and/or clinical treatment in the Graduate Endodontic clinic at Indiana University School of Dentistry. There are currently 7 endodontic residents enrolled in the graduate program who will be eligible to screen patients presenting to the graduate clinic for elective, urgent, or emergency endodontic treatment. If an endodontic resident other than the student researcher ([name]) diagnoses their respective patient's mandibular molar with symptomatic irreversible pulpitis, and all other inclusion/exclusion criteria are respected, then the student researcher will be eligible to further evaluate the patient and potentially include them in the study.

The study biostatistician will provide a two-product randomization scheme which will randomize each subject on the order of their entry into the study. Subjects will be randomized equally to the two treatments using a block randomization, participants receiving multiple root canal procedures will be treated as a single subject. 30 subjects per treatment will be enrolled. The randomization scheme will be provided to clinic assistants [name] and [name]. They will prepare each anesthetic solution behind closed doors and provide each carpule to the

[figure not shown]
researcher at every appointment. The stopper of every carpule, regardless of experimental group, will be punctured to remove bias. The study subject will be blinded to treatment assignment.

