## 7.0 Study Procedures

### Single Visit: Screening and Study procedure

1. Review medical history (about 3-5 minutes)
  - a. If previously on file, the patient will need to verbally confirm all forms are accurate
  - b. If the patient is new to IUSD, then the proper medical history intake form will be completed and confirmed by the patient, as per standard of care
  - c. Participants will be explained what an analgesic is, and will confirm they have not taken any within 6 hours prior to study participation
2. Customary sensibility testing, specifically cold and Electric Pulp Testing (EPT), will be completed to ensure a diagnosis of symptomatic irreversible pulpitis in a mandibular molar specifically on the same day that the warranted endodontic treatment is to be rendered (about 5-10 minutes) as per standard of care.
  - a. Prospective study participants will be given brief instructions on cold and EPT usage/expectations
  - b. A vital, asymptomatic, contralateral posterior tooth (ideally molar) will undergo cold and EPT testing prior to administering anesthesia to serve as an internal control
  - c. The pulpal diagnosis will be primarily confirmed using Endo-Ice
3. Review inclusion/exclusion criteria to ensure that the subject qualifies to continue with the study (about 3 minutes)
4. Perform consenting procedures for both the Non-surgical Root Canal Therapy (NSRCT) and the research study (about 5-10 minutes)
  - a. Study participants will receive a concise explanation regarding the nature of the 2 possible anesthetic formulations and the EPT testing intervals that are expected to follow. Participants will be explicitly notified that the anesthetic formulation will not affect the overall prognosis of the endodontic treatment needing to be rendered. Once profound anesthesia is confirmed, the NSRCT will proceed as usual and customary.
5. Randomize the subject to the type of anesthetic formulation (about 5 minutes)
6. Apply topical benzocaine jelly after thoroughly drying the tissues surrounding the Inferior Alveolar Nerve Block (IANB) injection site and the buccal vestibule of the tooth to be treated (about 1 minute), as per standard of care

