7. Administer **1 carpule** (1.8mL) of the previously determined formulation of 2% Lidocaine w/ 1:100k epi and 1 carpule of 3% Carbocaine plane via IANB, followed by 0.5 carpules (0.9mL) of 4% Septocaine with 1:100k epi via buccal infiltration and 0.5 carpules of 4% Septocaine with 1:100k epi via lingual infiltration (about 3 minutes)
8. Using a stopwatch, the student researcher will wait 3 minutes after administering anesthesia and then obtain the 2nd EPT reading on the tooth being treated, as well as assessing soft tissue anesthesia of the respective side of the mandible

- a. EPT=80 (maximum stimulation) without pulpal or soft tissue sensations indicates profound pulpal anesthesia and the endodontic access may be initiated
- b. EPT $\neq$ 80 with pulpal and/or soft tissue sensations indicates a need to wait additional time
9. Retest the tooth being treated using EPT at 2-minute intervals until EPT=80 or when 15 minutes have passed
  - a. Participants who did not demonstrate total soft tissue and/or pulpal anesthesia within 15 minutes will be categorized as a failure (lack of anesthetic profoundness), with time to anesthesia censored at 15 minutes. No additional study outcomes will be collected from the patients, who will be withdrawn from the study, and further managed according to the best clinical practice (additional block/supplementary injections) so that the endodontic treatment may continue appropriately
10. Patients who indicate any pain (excluding pressure) elicited from the tooth undergoing treatment upon endodontic access or a complete pulpotomy (after initially confirming pulpal anesthesia with the EPT) will also be categorized as a failure (lack of anesthetic profoundness), withdrawn from the study, and appropriately managed as previously described.
  - a. Visual Analog Scales (VAS) shown below will be used to report the patient's perceived discomfort at the end of treatment.

11. The student researcher will chart the data for each uniquely identified study participant regarding the initial EPT readings (treated tooth and control), the amount of time taken to reach both soft tissue and pulpal anesthesia, and the conditions that lead to a "failed" profoundness of anesthesia
  - a. A trained research assistant will separately record each patient's unique identifying code with the anesthetic formulation (buffered vs. unbuffered) that was prepared and administered

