## **11.0 Statistical Considerations**

The two groups will be compared for differences in the percentage of subjects who fail to achieve profound pulpal anesthesia using chi-square tests. The time needed to achieve profound pulpal anesthesia for the two groups will be compared using Kaplan-Meier survival curves and log-rank tests, with patients who fail to achieve profound pulpal anesthesia censored at 15 minutes. A logistic regression model for presence of profound pulpal anesthesia will be used to determine whether molar type (first, second, third molar) affects the group comparisons; the model will include both factors and their interaction. A similar Cox proportional hazards survival model will be used for the analysis of time needed to achieve profound pulpal anesthesia. VAS scores will be compared between treatments using a Wilcoxon Rank Sum test. A two-sided 5% significance level will be used for all tests.

With a sample size of 28 subjects per group, the study will have 80% power to detect a hazard ratio of 2.25 between the two groups for time to profound pulpal anesthesia, using calculations with a two-sided 5% significance level and based on a log-rank test with median time to anesthesia 10 minutes in the control group. Sample size calculations were performed using PASS 2019 (NCSS, LLC. Kaysville, UT). To account for up to 2 subjects per group with unusable data, the study will enroll 30 subjects per group.

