## **12.0 Statistical Data Management**

- Primary data will be collected via direct data capture from measurement instrument (Electronic Pulp Tester/EPT), time to profound anesthesia, molar type and VAS score and stored electronically in SPSS files on Department Server. The storage location will be backed up automatically every day.

- All other data will be stored in either a locked cabinet in the department of Endodontics that only the study team will have access to or on an encrypted, password protected computer that only the study team can access.
- Data summary sheets will be stored for use by the statistician using an IRB approved sharable method such as Microsoft One Drive.

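### No provision to record pre-treatment pain or severity: the secondary VAS comparison forgoes precision, and chance imbalance in starting pain stays unseen

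*Combined protocol and SAP*

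**What the plan says.** - **Who enters.** Section 4.1: "Must be experiencing signs of irreversible pulpitis (mild, moderate, or severe) in a vital mandibular posterior tooth". Section 6.0 describes the pool that residents may screen as "patients presenting to the graduate clinic for elective, urgent, or emergency endodontic treatment".
- **What is measured before randomisation.** Section 7.0, step 2: "Customary sensibility testing, specifically cold and Electric Pulp Testing (EPT), will be completed". The rest of steps 1 to 5 covers history, eligibility, consent and randomisation. No step asks for a pain rating.
- **When the VAS is taken.** It is a secondary outcome (Section 3.2.2). Step 10a says it "will be used to report the patient's perceived discomfort at the end of treatment". The text gives it no other use.
- **What is kept.** Step 11 charts data "regarding the initial EPT readings (treated tooth and control), the amount of time taken to reach both soft tissue and pulpal anesthesia", together with the conditions behind any failure. Section 12.0 lists the EPT measurement, "time to profound anesthesia, molar type and VAS score and stored electronically". Neither list names pre-treatment pain or the severity grade.
- **Who gives a VAS.** Under step 9a, patients not anaesthetised by 15 minutes are withdrawn and contribute no further outcomes.
- **Allocation and analysis.** Section 6.0 allocates equally in blocks and states no stratification by severity. Section 11.0: "VAS scores will be compared between treatments using a Wilcoxon Rank Sum test".

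**The concern.** The plan itself names a wide range of starting severity, then measures pain once, after treatment, and compares the arms with no reference to where patients began. Two things are at stake.

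First, if starting pain predicts pain at the end of treatment, its spread between patients adds to the error of the VAS comparison, and a baseline score could remove part of it.

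Second, in a trial of 30 per arm the arms can differ in starting pain by chance. Without a recorded baseline, nobody can show whether they did or allow for it. Initial EPT is charted, but it is a reading of electrical response and does not stand in for a pain score.

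**Working it through.** **The plan's own figure.** The documents give no size or power for the VAS. Their only such figure is 28 per group for the primary log-rank test (80% power, hazard ratio 2.25, two-sided 5%). Freedman's formula gives (1.960 + 0.842)² × (3.25/1.25)² = 7.85 × 6.76 = 53.1, or 54 events in two equal groups. That is 27 per group if every patient has an event, close to the stated 28. With the 15-minute limit applied, 28 per group gives about 76% power, which is a separate matter. Here those inputs serve only to estimate how many patients reach the VAS.

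**Step 1: patients with a VAS.** Inputs: control median 10 minutes and hazard ratio 2.25 (Section 11.0); 15-minute limit (Section 3.1.1); 30 per arm (Section 6.0). Added assumption: exponential times.
- Control, not anaesthetised by 15 minutes: 2^(−15/10) = 0.354. Remaining: 30 × 0.646 = 19.4, about 19.
- Buffered: 2^(−1.5 × 2.25) = 0.096. Remaining: 30 × 0.904 = 27.1, about 27.

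Withdrawals for pain on access (step 10) may lower both numbers.

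**Step 2: chance imbalance in starting pain.** In units of the baseline SD, the difference in means has SD √(1/n₁ + 1/n₂).
- 30 and 30: √(2/30) = 0.258. The chance of a gap above 0.5 SD (0.5/0.258 = 1.94) is about 5%.
- 19 and 27: √(1/19 + 1/27) = 0.299. The chance (0.5/0.299 = 1.67) is about 10%, before any selection effect.

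A gap of 0.5 SD would shift the expected VAS difference by r × 0.5 outcome SDs: 0 at r = 0, 0.05 at r = 0.1, 0.15 at r = 0.3 and 0.25 at r = 0.5.

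**Step 3: precision.** With linear adjustment, residual variance is multiplied by 1 − r², and the equivalent sample size by 1/(1 − r²). The detectable difference (80% power, two-sided 5%, Wilcoxon efficiency 0.955) is 2.80 × √[(1/n₁ + 1/n₂)(1 − r²)/0.955]. The value of r is assumed.

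| r | Variance removed | Equivalent n | Detectable, 30/30 | Detectable, 19/27 |
|---|---|---|---|---|
| 0 | 0% | ×1.00 | 0.74 SD | 0.86 SD |
| 0.1 | 1% | ×1.01 | 0.74 SD | 0.85 SD |
| 0.3 | 9% | ×1.10 | 0.71 SD | 0.82 SD |
| 0.5 | 25% | ×1.33 | 0.64 SD | 0.74 SD |

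On these assumptions, losing the 15-minute failures moves the detectable difference from 0.74 to 0.86 SD. Adjustment at r = 0.5 would only bring it back to where it began. For a rank-based adjustment, 1 − r² is an approximation, with r taken on the rank scale.

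**The case against.** A reader might infer that without a baseline the VAS comparison is biased or invalid. The documents do not support that. Allocation is randomised, so an unadjusted Wilcoxon test is valid among all randomised patients. Section 3.2.2 defines the endpoint as pain scores, not change in pain, so the plan does not ask a question that requires a baseline. The VAS is also secondary, and the primary log-rank test does not use it. All of this stands.

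The precision gain may also be small. On one reading of steps 9a and 10, only patients with an EPT of 80 and no pain on access remain to give a VAS. Their scores may lie near zero and correlate weakly with earlier tooth pain. That stands, and is why the table starts at r = 0.

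The larger threat to the VAS is that patients who give one are selected after randomisation, probably at different rates by arm. Baseline adjustment within that subset would not restore the randomised comparison and could look falsely reassuring. That stands too.

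Some of the evidence needs care. The range from elective to emergency cases describes whom residents screen and is not an eligibility rule; entry still requires the diagnosis. The step 11 list is not exhaustive, since it omits the VAS and molar type that Section 12.0 stores, and the VAS form itself is not visible. So the documents support saying that no visible text provides for a baseline pain record, and no more. The severity range in Section 4.1 is explicit, however, and nothing stated in Sections 7.0 or 12.0 captures it.

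**Conclusion.** The point holds as a cheap improvement to a secondary analysis and does not show an error of validity. The plan admits a stated range of severity, provides no visible record of it or of starting pain, and compares end-of-treatment VAS unadjusted. The cost is lost precision and an inability to see or correct chance imbalance.

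The size is uncertain. Variance saved runs from nothing at r = 0 to 25% at r = 0.5, and the documents give no value of r. The chance of a gap above 0.5 SD in starting pain is about 5% with 30 per arm. It is about 10% with the 19 and 27 expected to give a VAS, a split that rests on the plan's median and hazard ratio plus assumed exponential times. The case for recording and reporting baseline severity does not depend on r.

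**What to change.** 1. In Section 7.0, after consent (step 4) and before randomisation (step 5), have each patient mark the same VAS for current tooth pain, and record the mild, moderate or severe grade. Step 3 would be too early, because research consent has not yet been given.
2. Add both items to step 11 and Section 12.0.
3. Report both by arm, once for all randomised patients and once for those with an end-of-treatment VAS, so that selection can be described.
4. In Section 11.0, prespecify one analysis: a rank-based ANCOVA of end-of-treatment VAS on pre-treatment VAS, with the unadjusted Wilcoxon test as support. State that adjustment does not correct for the missing scores of 15-minute failures.

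**Cost:** under a minute per patient, two data fields and a few sentences of text. The precision gain may be slight if end-of-treatment scores cluster near zero. Current pain cannot be recovered reliably once treatment has begun, so the change should be made before enrolment starts or, failing that, for the patients still to be enrolled.

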**3.0      Outcome Measures/Endpoints**

**3.1      Primary Outcome Measures**

**3.1.1** The primary outcome is to gauge the time it takes for the buffered anesthetic to provide profound anesthesia, displayed by an EPT reading of 80. The time will be censored at 15 minutes if profound anesthesia is not achieved within 15 minutes.

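### The primary log-rank test is valid but unadjusted, and the treated tooth's pre-randomization EPT reading is used in no analysis

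*Combined protocol and SAP*

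**What the plan says.** **Endpoint.** Section 3.1 defines the primary outcome as the time until the EPT reads 80, and adds: "The time will be censored at 15 minutes if profound anesthesia is not achieved within 15 minutes". Section 7.0 (steps 8 and 9) fixes the readings at 3 minutes and then every 2 minutes up to 15.

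**Primary comparison.** Section 11.0 has time in the two groups "compared using Kaplan-Meier survival curves and log-rank tests". No covariates or strata are named. Section 6.0 describes equal block randomization without a stratification factor.

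**Initial EPT.** In Section 7.0, cold and EPT testing is step 2 and randomization is step 5. Step 8 calls the 3-minute measurement the second reading on the treated tooth, so the first precedes the anesthetic. Step 11 has the researcher chart "the initial EPT readings (treated tooth and control" teeth. Section 11.0 does not mention these values.

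**Molar type.** Section 12.0 lists "time to profound anesthesia, molar type and VAS score" among the stored data. Section 11.0 plans a logistic model "to determine whether molar type (first, second, third molar) affects the group comparisons", and states that "the model will include both factors and their interaction". For the time endpoint it adds: "A similar Cox proportional hazards survival model will be used for the analysis of time needed to achieve profound pulpal anesthesia".

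**Sample size.** Section 11.0 claims 80% power with 28 per group for a hazard ratio of 2.25, with a control median of 10 minutes, a log-rank test and a two-sided 5% level. Enrollment is 30 per group.

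**The concern.** The event is a reading of 80, and the initial reading is the starting value of that same measurement on the same tooth. It is a natural candidate for a prognostic baseline variable, and it costs nothing extra to collect because it is already charted. With about 30 patients per group and no stratification, the standard error of a standardized baseline difference is √(2/30) = 0.26 SD, so an imbalance of 0.25 SD or more would arise in about one trial in three.

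The stake is power. If the starting value predicts onset time, an unadjusted comparison leaves that variation in place. The trial has little power to spare, as the first step of the working shows.

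**Working it through.** **Step 1: the plan's own figure.** Inputs from Sections 3.1 and 11.0: HR 2.25, control median 10 minutes, censoring at 15 minutes, 28 per group, two-sided 5%. Exponential times are assumed.

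- Event probability, control: 1 − exp(−ln 2 × 15/10) = 0.646.
- Event probability, buffered: 1 − exp(−2.25 × ln 2 × 15/10) = 0.904.
- Expected events: 28 × (0.646 + 0.904) = 43.4.
- Schoenfeld events needed: 4 × (1.960 + 0.842)² / (ln 2.25)² = 47.7, so 48, or 48/1.550 = 31 per group.
- Power with 43.4 events: Φ(√43.4 × 0.811/2 − 1.960) = Φ(0.71) = 76%.

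The Lakatos method gives 75.8%. The stated 80% is therefore not reproduced under 15-minute censoring. Schoenfeld with 20 minutes of follow-up would give 80.0%. The starting point for the comparison below is about 76%.

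**Step 2: adjusted against unadjusted power.** Trials of 28 per group were simulated on the 3, 5, …, 15-minute grid, with one standard-normal baseline covariate standing for the initial EPT reading. The tests were the log-rank test and the treatment term of a Cox model (Efron ties) containing treatment and the covariate. Its log-HR per SD is an assumption, shown as a range. Two calibrations were used, because the stated HR of 2.25 could be read as either a marginal or a conditional effect.

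| Log-HR per SD | Marginal HR 2.25: log-rank | Adjusted Cox | Change (points) | Conditional HR 2.25: log-rank | Adjusted Cox | Change (points) |
|---|---|---|---|---|---|---|
| 0 | 76.5% | 75.1% | −1.4 | 77% | 75% | −2 |
| 0.2 | 76.6% | 77.1% | +0.5 | 73% | 74% | +1 |
| 0.35 | 75.9% | 80.1% | +4.2 | 69% | 74% | +5 |
| 0.5 | 74.9% | 82.9% | +8.0 | 63% | 72% | +9 |

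The marginal set used 4,000 trials per row, so each power has a Monte Carlo standard error of about √(0.75 × 0.25/4000) = 0.7 points. Differences of one point or so should not be over-read. A separate run of 1,200 trials at conditional HR 2.25, comparing Wald tests with and without the covariate, also gave 63% against 72% at 0.5.

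**Step 3: type I error.** In the marginal set it was 5.0% to 5.3% for the adjusted Cox test and 5.4% to 5.5% for the log-rank test. In the conditional set both were about 4.5% to 6%.

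**Step 4: does the planned molar-type model already do this?** It omits the EPT reading, and with an interaction its group term is the effect in the reference molar, not an overall adjusted effect. With an assumed 50/40/10 mix of molars and conditional HR 2.25, that term had about 46% power. A main-effects Cox model with molar type alone, against the log-rank test, gave 73.9% against 75.8% with no molar effect, 74.7% against 75.2% at log-HR ±0.3, and 74.7% against 69.8% at ±0.6.

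**The case against.** The strongest reply is that nothing here is an error. Under randomization the log-rank test is valid, chance imbalance does not bias it, and its type I error already allows for such imbalance. An unadjusted test also matches unstratified randomization. All of that stands.

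Next, no section links the initial EPT reading to onset time. Section 7.0 scores the event as a threshold state, and confirms the diagnosis primarily by cold testing. This stands too, and is why the gain is given as a range that includes a small loss.

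Third, a Cox model brings in proportional hazards and a linear EPT term on about 43 events, and changes the estimand to a conditional hazard ratio. The published sample size also refers to a log-rank test. These are real costs. They are softened because that calculation already rests on a single hazard ratio, Section 11.0 already plans a Cox model for this endpoint, and a covariate-adjusted log-rank test is available. Listing the adjusted analysis only as supportive would avoid these costs, but would leave the power of the primary test unchanged.

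A reader might go further and infer that adjustment is free, so that unknown prognostic strength does not matter. The first row of the table shows a loss of 1 to 2 points instead. A reader might also infer that molar type is ignored. It is already in a planned Cox model, and adding it as a main effect gains nothing unless its effect is large.

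**Conclusion.** The point holds as a recommendation on efficiency. The primary test is valid but unadjusted, and a pre-randomization measurement on the endpoint's own scale enters no analysis. Adjusting for it at 28 per group changes power by about −1 to −2 points if it is not prognostic, 0 to +1 at log-HR 0.2 per SD, +4 to +5 at 0.35, and +8 to +9 at 0.5. These figures assume exponential times, proportional hazards, a single linear covariate and a prognostic strength that the documents do not give. They were computed for the Cox model, not for a covariate-adjusted log-rank test.

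Three stronger conclusions are not supported. The planned comparison is not biased or invalid. The smaller unadjusted hazard ratio that appears when a prognostic covariate is left out reflects a marginal rather than a conditional quantity, not bias in the marginal estimate. And the case does not extend to a multi-covariate logistic model for failure: under the plan's inputs about 28 × (1 − 0.646) + 28 × (1 − 0.904) = 12.6 failures are expected before any failures from pain on access, too few for several terms.

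**What to change.** In Section 11.0, before unblinding:

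- Make the primary treatment test a main-effects Cox model with treatment and the treated tooth's initial EPT reading as a linear term, stating how ties are handled; or a covariate-adjusted log-rank test using the same reading.
- State which reading is used if a tooth has more than one before anesthesia, since Section 14.0 allows screening and treatment on separate visits.
- Keep the Kaplan-Meier curves and the unadjusted log-rank test as supportive.
- Keep the molar-type interaction model for the secondary objective only. Molar type need not enter the primary model, and the failure comparison needs no added covariates.

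The cost is wording; the data are already charted. The downsides to accept are a power loss of 1 to 2 points if the reading proves uninformative and, if the Cox model is chosen, reliance on proportional hazards and linearity and a covariate-conditional hazard ratio. While Section 11.0 is open, the sample size paragraph should state its follow-up time and method, since 15-minute censoring gives about 76% power at 28 per group.
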